Heart Rate Variability Biofeedback (HRVB) is a biobehavioral intervention involving rhythmic breathing at resonance frequency (**RF**) that stimulates the baroreflex to offset these psychophysiological deficits. The autonomic normalization effected by RF breathing is believed to bolster cognitive control efforts by interrupting or dampening automatic-visceral reactions that can unintentionally undermine treatment gains, and in doing so support better decision-making, motivation, reductions in craving, and shifts in attention allocation ¹⁵. HRVB's capacity to help individuals better regulate affect and bolster cognitive control has garnered excitement in addiction clinical science ^{3, 16, 17}, and preliminary studies suggest HRVB could be a valuable addendum to first-line addiction treatments ^{15, 18-24}.

Studies of first-generation HRVB focused on positive cognitive and behavioral effects that accrue over weeks or months of regular, daily RF breathing practice. However, recent studies have demonstrated that a brief exposure to RF breathing in anticipation of psychosocial stress, or during induced stress, helps to control physiological arousal, reduce state anxiety, and improve cognitive performance ^{15, 25, 26}. Our clinical observations provide further support for in-the-moment

RF breathing. We have observed many HRVB study participants intuitively use RF breathing to manage intense, momentary negative affect, even though they were not explicitly instructed to do so^{18, 24}. We posit that such in-the-moment bursts of HRVB practice could be an SUD treatment tool that helps individuals buffer salient triggers and urges to use AOD in-the-moment.

Recent advances in the field have given rise to small, lightweight, wearable biosensors that can allow wearers to do HRVB on-the-go. These second-generation HRVB devices can also function as a just-in-time interventions by prompting in-the-moment HRVB practice when autonomic hyperarousal is detected, to buffer salient triggers and urges to use AOD. In addition to their potential for direct clinical benefit, the advent of these second-generation, ambulatory, HRVB devices has implications for the accessibility and scalability of HRVB because these devices are affordable, accessible, integrate with the end-user's smartphone, and do not require a provider to administer the intervention.

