This study builds on a body of preliminary work speaking to HRVB's potential as an addendum to first-line SUD treatments. We will be using the 'Lief Smart Patch' device in this research (<https://getlief.com>). The Lief Smart Patch is a small, wearable, electrocardiogram (ECG)-based heart rate monitor that is attached to the body utilizing skin safe ECG electrodes. ECG technology is known to be safe and carries no substantial risk. The device monitors heart rate variability (HRV) as an index of autonomic nervous system arousal and can prompt the wearer to engage in brief bursts of HRVB practice via a connected smartphone app when stress is inferred. Wearers are also able to engage in regularly scheduled HRVB practice, and practice *ad libitum*. The Lief biofeedback device is being used in this study to deliver a clinical intervention and collect physiological data; the effectiveness of the device itself is not being tested.

2. Specific Aims and Objectives

The aim of this pilot study is to administer heart rate variability biofeedback (HRVB) to adults with substance use disorder who are receiving outpatient treatment as usual (TAU) and compare them to a control group receiving TAU only on intervention outcomes that include alcohol/drug use and negative affect. The study's specific aims are as follows:

[figure not shown]
- Aim 1:** Assess ambulatory HRVB's uptake by individuals with SUD in terms of practice time, and perceived barriers to uptake based on qualitative participant feedback (proof-of-concept)
- Aim 2:** Test effects of HRVB practice on affect and substance use
 - a.** Test day-level effects of HRVB practice on affective states and substance use
 - b.** Test the accumulative, person-level effects of scheduled daily HRVB practice vs. in-the-moment HRVB practice, vs. their interaction on substance use during the 8-week intervention period

We hypothesize that participants receiving HRVB + TAU will have a lower alcohol/drug use lapse rate and demonstrate greater reductions in negative affect compared to controls receiving TAU only.

3. General Description of Study Design

Design Overview

We will recruit 120 adults with substance use disorder (SUD) in their first year of a current SUD recovery attempt. Participants will be randomized using the SAS statistical program to either the experimental ($n= 70$) or control group ($n= 50$). We will also recruit 10 experimental group participants to participate in focus groups ($n= 5$ in each).

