Experimental group participants will participate in 8 weeks of HRVB training using the Lief HRVB biopatch and smartphone app, and 2x daily ecological momentary assessment of affect and substance use. Participants will also be encouraged to self-initiate ecological momentary assessment surveys when feeling high levels of stress or craving. Experimental group participants will be encouraged to wear the Lief HRVB biopatch for at least 8 hours per day and use it as needed to regulate negative affect in-the-moment with a minimum of 5mins daily *ad hoc* practice, and 5min of scheduled HRVB practice twice daily, for a total of 15min daily practice.

The control group will participate in 8 weeks of 2x daily ecological momentary assessment of affect and substance use. Participants will also be encouraged to self-initiate ecological momentary assessment surveys when feeling high levels of stress or craving. Both groups will be allowed to continue with whatever SUD treatment they are independently engaged in. In other words, we will not ask participant to desist any existing treatments they are utilizing.

4. Subject Selection

Participants

Participants will be 120 adults ≥ 18 years of age in the first year of a current SUD recovery attempt. To reduce the likelihood of acute substance withdrawal symptoms influencing affect and physiological indices, participants will be required to have at least two weeks of abstinence from alcohol and other drugs immediately prior to study participation. To allow for recruitment of a representative sample of individuals in early recovery from SUD, commonly co-occurring psychological conditions such as affective disorders and PTSD will be allowed. Medications will be allowed. However, individuals with severe cardiac arrhythmias which would confound HRV

analyses will be excluded, as will persons with active psychosis.

Recruitment Procedures

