Then, after experimental participants receive their device, they will have the option of communicating as often as they want with their coach in the Lief app's chat box. Coaches aim to respond within a business day (asynchronous communication). Participants will also have the option of scheduling 20min, *ad hoc* coaching sessions with one of Lief's coaches. Importantly, these HRVB phone coaching sessions are not psychotherapy, nor are they designed to replace psychotherapy, and Lief's coaches are trained to only offer support related to HRVB.

Throughout the 8-week study protocol, all study participants will have as needed access via phone and text to the study research coordinator, should issues with the ecological momentary assessment application arise, or the participant has any other questions or concerns. This will be a convenient channel through which participants can contact research staff for technical assistance, however, research staff may contact participants to check apps are functioning properly, for instance, in the event a participant has missed a lot of ecological momentary assessment surveys. We will use the MGB Cisco Jabber messaging app to create a unique study contact number at which the study research coordinator can be reached.

The heart rate variability biofeedback intervention

The HRVB equipment in this study includes a wearable ECG monitor (known as the Lief Smart Patch) and a smartphone app.

The Lief Smart Patch is a wearable, ECG-based heart rate monitor. It is attached to the body utilizing skin-safe ECG electrodes. ECG technology is known to be safe and carries no substantial risk. The Smart Patch senses stress and anxiety in real time based on HRV and breathing patterns, and then provides a breath-based heart rate variability biofeedback intervention. The Smart Patch collects heart rate, heart rate variability, and accelerometer data through continuous monitoring. These data are synced with the end-user's smartphone via Bluetooth Low Energy, then encrypted and sent through their wireless network to Lief's HIPAA-compliant server. This device does not collect data on geo-location, nor does it have any participant information stored on it. If a device is lost, there is no risk to participants of a privacy breach.

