Experimental group participants will use the complementary Lief smartphone app to engage in the 8 weeks of HRVB. The Lief app is compatible with iOS and Android devices and provides a visual interface that supports HRVB practice. It also includes architecture that allows end-users to schedule *ad hoc* phone coaching sessions.

Focus groups

Experimental group participants ($N= 10$) will participate in 60-minute, audio-recorded focus groups moderated by the PI. There will be two groups of 5. These focus groups will gather feedback on participant interest in ambulatory HRVB, perceived benefits, and barriers to practice/device use.

Participant Compensation

To encourage study completion, participants ($N= 120$) will be compensated with an Advarra gift card loaded in installments.

The compensation breaks down as follows: Participants will be compensated \$50 for completing the study intake/orientation and baseline questionnaire measures. They will also be compensated \$100 for completing the ecological momentary assessment component of the study (defined as completing surveys every week of the 8-week study period), with a \$100 bonus payment for achieving $\geq 90\%$ ecological momentary assessment survey completion over the whole 8-week study period. Also, to motivate the return of ECG monitors and give the experimental group extra compensation for their additional work in the study, the experimental group will also receive a \$100 bonus for return of study equipment. Participants who participate in the focus group will also be compensated \$50.

The \$50 for completing the study intake session will be provided immediately following the intake session. The remainder of the compensation will be electronically added to participants' Advarra gift card at the end of the 8-week study period.

Sending and Receiving Data

Lief Therapeutics will provide the PI [name] with the participants' physiology data, including heart rate variability, wear time, and paced-breathing practice time. This physiology data will be available for download from the Lief participant dashboard. The deidentified data file will be sent to the study email for direct download and saved to the study drive for analysis. Participant data that the study team cannot directly download will be retrieved by Lief Therapeutics and shared to the study team using a secure, MGB DropBox account.

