All research staff at the MGH Recovery Research Institute are fully trained in relevant ethical principles and procedures, including maintaining confidentiality, and are certified by Collaborative Institutional Training Initiative (CITI) to conduct research with human subjects. During the study, we will notify officials, as mandated by law, if a participant reports intentions to harm himself/herself or others, or reports child or elder abuse. Participants will be informed of these limits to confidentiality during the consenting process. Serious adverse events will be reported to the MGH Institutional Review Board immediately by telephone and by written report within 24 hours of our receipt of information regarding the event.

8. Benefits

A potential participant benefit for the experimental group is improved substance use and affective outcomes. A potential participant benefit for both the experimental and control groups may be increased awareness of personal patterns in affect through the conduct of ecological momentary assessment.

There are also considerable benefits to society associated with this study. Substance problems carry a tremendous emotional, medical, interpersonal, and societal cost. The knowledge gained in this study may lead to the adoption of a novel SUD treatment tool that bridges gaps in existing treatment approaches. The minimal risks associated with this research are reasonable given the potential benefits of this study.

9. Statistical Analysis

Because this is a pilot study with limited power to detect statistical significance, we will focus on interpreting effect sizes to inform a subsequent R01 trial. We note however, certain design strengths that will allow us to maximize statistical power. For instance, in our regression models, rather than just looking at main effects of group, we will also assess Heart Rate Variability Biofeedback (HRVB) practice time as a continuous measure with controls scored as 0. Additionally, power to test day-level associations is boosted by the repeated measures design with up to 84 repeated, momentary assessments per participant.

Please note that we use the term “day-level” below to denote effects at the level of individual ecological momentary assessment (EMA) surveys. From this perspective we have up to 84 repeated, momentary assessments of affect and substance use.

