Using multilevel models where days (L1) are nested within persons (L2), we will explore the effects of day-level HRVB practice earlier in the day (i.e., lagged) on subsequent day-level negative affect (**Model 1**), craving (**Model 2**), positive affect (**Model 3**), and substance use (yes/no; **Model 4**), while also testing whether HRVB decouples the anticipated relationship of day-level negative affect (**Model 5**) and craving on subsequent substance use (**Model 6**).

In models 1-3 (multilevel linear regression models), the dependent variables will be day-level negative affect scores, day-level craving scores, and day-level positive affect scores, with lagged day-level minutes of scheduled practice, and lagged in-the-moment HRVB practice (with controls' HRVB practice coded as 0), and their interaction term (lagged scheduled practice \times lagged in-the-moment practice) as the independent variables, controlling for age, sex, nicotine use (yes/no), medications known to affect the cardiovascular system (yes/no), and baseline past-month AOD use (percent days abstinent).

A priori, we anticipate that both greater daily scheduled HRVB practice and in-the-moment HRVB practice will predict lower subsequent day-level negative affect and craving, and that their interaction will indicate additive benefits of combining scheduled and in-the-moment practice. The relationship between positive affect and HRVB has not previously been explored, so we will treat this aspect of the analysis as exploratory. Our benchmark for preliminary demonstration of treatment benefit will be semi-partial R²'s for practice time of $\geq .10$ (medium effect size).

Models 1-3

Negative affect = day-level scheduled HRVB practice_{t-1} + day-level in-the-moment HRVB practice_{t-1} + [day-level scheduled HRVB practice_{t-1} * day-level in-the-moment HRVB practice_{t-1}] + age + sex + nicotine use + medications known to affect the cardiovascular system + baseline past-month AOD use + error

Craving = day-level scheduled HRVB practice_{t-1} + day-level in-the-moment HRVB practice_{t-1} + [day-level scheduled HRVB practice_{t-1} * day-level in-the-moment HRVB practice_{t-1}] + age + sex + nicotine use + medications

*known to affect the cardiovascular system + baseline past-month AOD use
+ error*

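### Models 1-4 omit the state that prompts in-the-moment practice, the negative-affect hypothesis has no written group model, and Model 7's practice terms have no time order

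*Combined protocol and SAP*

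**What the plan says.** **What triggers practice.** Section 1 describes these devices as "prompting in-the-moment HRVB practice when autonomic hyperarousal is detected" and says the study device "can prompt the wearer to engage in brief bursts of HRVB practice via a connected smartphone app when stress is inferred". Section 6 adds that the patch "senses stress and anxiety in real time based on HRV and breathing patterns". Section 3 asks participants to "use it as needed to regulate negative affect in-the-moment with a minimum of 5mins daily", so the link to state is partial: some in-the-moment practice is expected every day regardless.

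**Models 1-4 (Section 9, Aim 2a).** The plan states: "we will explore the effects of day-level HRVB practice earlier in the day (i.e., lagged) on subsequent day-level negative affect". Negative affect, craving, positive affect and substance use are each regressed on lagged scheduled practice, lagged in-the-moment practice and their product. The covariates are age, sex, nicotine use, cardiovascular medication and baseline percent days abstinent (PDA). No earlier affect, craving, arousal or use is included.

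**Models 5-6.** These add lagged negative affect and, in Model 6, lagged craving. The outcome is substance use only, the two kinds of practice are summed, and practice and affect share the index t-1.

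**Group comparisons.** Section 2 hypothesises that the HRVB arm will "demonstrate greater reductions in negative affect compared to controls receiving TAU only". The opening of Section 9 says "in our regression models, rather than just looking at main effects of group, we will also assess" practice time. A sentence giving a group version is attached to Models 4, 5, 6 and 7, but not to Models 1-3.

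**Model 7 (Aim 2b).** PDA over the 8 weeks is regressed on total practice of each kind. Greater practice is expected to go with greater PDA, and a semi-partial R² of at least .10 is the benchmark for benefit.

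**The concern.** Lagging practice puts it before the outcome, but it does not remove the earlier state that led to the practice. Someone who is distressed at one survey is more likely to practise next and, if distress persists, to report distress at the following survey. The in-the-moment coefficient then mixes the effect of practice with that persistence. Section 9 expects negative affect to predict later use, so Model 4 is open to the same problem.

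The documents do not tie scheduled practice to stress, so the two kinds of practice may be biased differently. Comparing them is a stated aim.

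A randomised comparison avoids this confounding, but for negative affect the only equation written is the practice one. In Model 7 a lapse early in the 8 weeks could change later practice, which creates an association even if HRVB does nothing. Section 9 says effect sizes from this pilot will inform the next trial, so bias in them matters more here than significance does.

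**Working it through.** **The plan's own figures.** For Aim 2b, a noncentral F calculation with N = 100, 8 predictors, 3 tested terms, 5% alpha and 80% power gives f² = 0.114. Then R² = 0.114/1.114 = 0.102, which matches the stated .10. For Aim 2a, r = 0.15 with 8,300 observations treated as independent gives power of about 100%, which matches the stated >99%. Neither figure depends on this point.

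**Model 1, practice triggered by the surveyed state.** All inputs below are assumptions: affect autocorrelation ρ, log-odds of practice per SD of worse affect, and within-person SD 0.77 (= √0.6). Let Δ be the difference in prior affect, in within-person SDs, between windows with and without practice. Approximately:

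planned coefficient = true effect + ρ × Δ × 0.77

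With practice in roughly 40% of windows, Δ is 0.47 at log-odds 0.5 and 0.83 at log-odds 1.0. The table compares the formula with a simulation (100 people in the 70:50 ratio, 84 surveys).

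| ρ | log-odds | ρ × Δ × 0.77 | simulated, true effect 0 | simulated, true effect -0.20 | same, prior affect added |
|---|---|---|---|---|---|
| 0.2 | 0.5 | 0.07 | +0.07 | -0.13 | -0.20 |
| 0.2 | 1.0 | 0.13 | +0.12 | -0.08 | -0.20 |
| 0.4 | 0.5 | 0.14 | +0.14 | -0.06 | -0.20 |
| 0.4 | 1.0 | 0.26 | +0.25 | +0.04 | -0.20 |
| 0.6 | 0.5 | 0.22 | +0.21 | +0.01 | -0.20 |
| 0.6 | 1.0 | 0.38 | +0.36 | +0.15 | -0.20 |

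If practice does not depend on affect, both forms are unbiased.

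**Model 1, practice triggered by arousal between surveys.** This is closer to a real-time prompt. A separate simulation (70/50, random intercept, 10% of surveys missed, ρ 0.2-0.6, log-odds 0.25-1.5, true effect -0.20 within-person SD) gave -0.09 to +0.56 for the planned form and -0.13 to +0.21 with prior affect added. The sign stayed wrong in 6 of 12 scenarios after adjustment.

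**Model 4.** With a true odds ratio of 0.75, the planned form gave 0.73 to 1.09. Adding prior negative affect and use gave 0.71 to 0.80 (survey trigger) or 0.77 to 0.91 (between-survey trigger). Craving was not simulated.

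**Why the order must be stated.** If practice indexed t-1 happens before survey t-1, adjusting for affect at t-1 removes part of the effect. In simulation it left 0.00 to -0.03 of a true carry-over of -0.04 to -0.12.

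**Why lagged terms must stay out of group versions.** With a stable group effect δ and autocorrelation ρ, conditioning on the previous outcome leaves a group coefficient of (1 - ρ)δ. That is 80%, 60% and 40% of δ at ρ = 0.2, 0.4 and 0.6; random-intercept simulations agree.

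**Model 7, no HRVB effect.** The table gives the share of simulated trials that reach R² ≥ .10 with both slopes in the anticipated direction (N = 120, 56 days, adherence SD 0.25, use on half of days after a lapse; all behavioural inputs assumed).

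| Practice after a lapse | 20% lapse | 40% lapse | 60% lapse |
|---|---|---|---|
| unchanged | 0.1% | 0.1% | 0.1% |
| halved | 0.2% | 9% | 37% |
| down 80% | 3% | 45% | 89% |

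If practice rises by 50%, R² alone is met in 20/31/25% of trials, but in 0% once direction is required. The rates are fragile: at 40% lapsing and halved practice, two other set-ups gave 2% and 38%. The group test rejected in 4-6%.

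**The case against.** The plan is a pilot that calls these analyses exploratory and reads effect sizes, not p-values. Models 1-4 already have time order through the lag. Models 5-6 carry prior negative affect and craving. Model 7 adjusts for baseline PDA, has a group version and states the expected direction, so a harmful slope is unlikely to be read as success. Every size above rests on assumed persistence, trigger strength, lapse rate and post-lapse behaviour, and the daily minimum weakens the trigger.

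Much of this limits the point without removing it. The sizes are illustrations, and the direction rule for Model 7 is mostly clarification. But the lag does not adjust for prior state, and Models 5-6 neither cover affect outcomes nor separate the two kinds of practice.

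A reader might infer that no randomised analysis of negative affect is planned. That is too strong: the opening of Section 9 announces main effects of group in its regression models, and Models 1-3 are regression models. What is missing is an explicit sentence or equation. A reader might also infer that Models 1-4 will manufacture benefit. In Models 1, 2 and 4 the expected bias runs the other way, towards a missed benefit.

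**Conclusion.** The point holds as a gap in specification and adjustment.

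- The in-the-moment estimate in the practice versions of Models 1-4 is confounded by the state that prompted practice, provided affect persists between surveys. In Models 1 and 2, and in Model 4 if negative affect raises use, the push is towards no benefit or apparent harm. Model 3 has the same gap, but the plan treats it as exploratory and no direction is claimed here.
- The size cannot be computed from the documents, which give neither the persistence of affect nor the strength of the trigger.
- The negative-affect hypothesis has no explicit randomised model.
- Model 7's practice terms can show an association with no HRVB effect if practice falls after a lapse. The documents do not say that it does, so they do not support calling a positive Model 7 result false; the simulated rates show only that the error is possible. Its group version is unaffected, on the reading that group replaces the practice terms.

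This should be fixed before analysis. Confidence is high in the reading of the text and low in any particular magnitude.

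**What to change.** 1. **Practice versions of Models 1-4.** Define the practice window as the interval between survey t-1 and survey t. Add the state from the last survey before that window: the same outcome in Models 1-3; use, negative affect and craving in Model 4. State the same order for Models 5-6. Craving is one of the five items in the negative-affect index, so these two adjusters overlap and should not be interpreted separately.
2. **Group versions.** Write them out for Models 1-3. State that the group versions of Models 1-4 contain no lagged affect, craving, use or other post-randomisation term. This must be explicit, because the plan forms a group version by swapping group for practice and would otherwise carry the new lagged terms across. Base the treatment-effect conclusion on the group versions of Models 1-4 and 7, and report practice-time results as associational.
3. **Model 7.** Label the practice-time terms associational and count R² ≥ .10 only if the slopes are in the anticipated direction. An analysis of weeks 1-4 practice on weeks 5-8 PDA is not needed, or should be optional and descriptive. In simulation it was jointly significant in 3-10% of trials with an assumed effect and 4-12% with none, so it does not separate the two.

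**Cost.** These are wording changes on data already planned. Some rows are lost when the prior survey is missed. The bonus for at least 90% "ecological momentary assessment survey completion over the whole 8-week study period" implies that missed surveys are expected. Using the plan's 84 surveys:

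- 10% missed: 84 × 0.9 = 75.6 rows fall to 83 × 0.81 = 67.2.
- 20% missed: 84 × 0.8 = 67.2 fall to 83 × 0.64 = 53.1.
- Lag confined to the same day, 10% missed: 42 × 0.9 = 37.8 fall to 42 × 0.81 = 34.0.

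Group estimates will be imprecise: in the Model 1 simulations their SD was about 0.10, 0.15 and 0.23 at ICC 0.2, 0.4 and 0.6, with the wrong sign in 4-30% of single trials. Section 9 (Aim 1) accepts that affect between surveys is not fully observed, so some confounding will remain.
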